Current therapy for indolent non-Hodgkin's lymphoma show high overall response rates but with some toxicity. A common regimen uses fludarabine, mitoxanterone, decadron and rituximab which produces over 90% overall response rate but with 20% prolonged bone marrow toxicity and myelodysplastic syndrome. To improve on these results, we plan to treat subjects with combination with rituximab which targets tumor cells and the immunomodulator analog lenalidomide that targets both the tumor cell and the cancer cell environment. This combination shows synergy in killing of lymphoma cells and minimal overlapping toxicity.

STUDY OBJECTIVES:

Primary:

To evaluate the overall response rate of lenalidomide in combination with rituximab in previously untreated indolent non-Hodgkin's lymphoma

Secondary:

To evaluate the toxicity of lenalidomide in combination with Rituximab in previously untreated indolent non-Hodgkin's lymphoma.

STUDY DESIGN: A open label Phase II single institution study of Lenalidomide in combination with rituximab in subjects with previously untreated indolent non-Hodgkin's lymphoma.

STUDY ENDPOINTS

Primary: To determine the number of CR, PR, and progression-free survival.

Secondary: Determine the type, frequency, severity, and relationship of adverse events to lenalidomide and rituximab.

STUDY DURATION: 1 year	TOTAL SAMPLE SIZE: 155
DOSING REGIMEN(S):	STUDY DRUG SUPPLIES:
Schedule A: Lenalidomide 20 mg po daily, with escalation up to 25 mg on days 1-21 of 28 day cycle for patients with follicular and marginal zone lymphoma. Rituximab 375mg/m2 IV x1 on day 1 of every cycle Total 6 cycles. -and- Lenalidomide 10 mg po daily, with escalation up to 25 mg on days 1-21 of 28 day cycle for patients with a diagnosis of small lymphomocyctic lymphoma. Rituximab 375mg/m2 IV x1 on day 1 of every cycle Total 6	For study participants, Celgene Corporation will provide lenalidomide at no charge through the RevAssist® program.

cycles.

Patients with evidence of tumor response after 6 cycles can remain on treatment for a total of 12 months.

Schedule B:

Lenalidomide 20 mg po daily, with escalation up to 25 mg on days 2-22 of 28 day cycle for patients with follicular lymphoma for cycles 1-6. Lenalidomide 10mg po daily for days 2-22 for cycles 7-12. Rituximab 375mg/m2 IV x1 on day 1,8,15 and 22 of cycle 1 and on day 1 of every subsequent cycle. Total 12 cycles. -and-

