Severe rash has been reported following lenalidomide use. Although this rash is usually mild and resolves, there have been reported cases of severe reactions, and in some cases this has lead to death.

Complete and updated adverse events are available in the Investigational Drug Brochure and the IND Safety Letters.

Rationale for Treatment in this Setting

Current therapy for indolent non-Hodgkin's lymphoma: The optimal treatment of indolent non-Hodgkin's lymphoma has not been determined. While indolent non-Hodgkin's lymphoma responds to many drugs, there is no best combination that offers efficacy with minimal toxicity. Combination chemotherapy such as fludarabine novanterone decadron and rituximab provide greater than 95% response rates; however, long term myelosuppression can be observed in 20% and secondary cancer occur in 5%. There is a need for better options. Rituximab consistently improves response rates in non-Hodgkin's lymphoma. The immunomodulator lenalidomide targets the cancer cell environment. Rituxan appears a rational combination with expected synergistic activity and minimal overlapping toxicity.

4. Study Objectives and Endpoints

Objectives

Primary objectives

To evaluate the overall response rate of lenalidomide in combination with rituximab in previously untreated indolent non-Hodgkin's lymphoma

Secondary study objectives

To evaluate the toxicity of lenalidomide in combination with Rituximab in previously untreated indolent non-Hodgkin's lymphoma

Endpoints

Primary Endpoint

To determine the number of CR, and PR.

Secondary Endpoints

Determine the type, frequency, severity, and relationship of adverse events to lenalidomide and rituximab.

5. Investigational Plan

Overall design

Patients will be stratified into 3 subgroups based upon their diagnosis. The three groups are defined as follicular lymphoma, marginal zone lymphoma, and small lymphocytic lymphoma (SLL). Up to 30 patients will be enrolled in the marginal zone lymphoma group, 45 patients small lymphocytic group (30 schedule A, and 15 Schedule B), and 80 patients (50 schedule A, 30 schedule B) will be enrolled in the follicular lymphoma group. Groups will continue to screen and enroll patients until maximum accrual is reached or evidence of unacceptable toxicity or lack of response is observed (see section 10; biostatistical analysis, for stopping rules).

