The sponsor shall notify the FDA by telephone or by fax of any unexpected fatal or life threatening experience associated with the use of the drug. As soon as possible, but no later than 7 calendar days after the sponsors initial receipt of the information. Each phone call or fax shall be transmitted to the FDA new drug review division in the Center for Drug Evaluation and Research or the product review division in the Center for Biologics Evaluation and Research that has responsibility for review of the IND if applicable.

Adverse event updates/IND safety reports

Celgene shall notify the Investigator via an IND Safety Report of the following information:

- Any AE associated with the use of study drug in this study or in other studies that is both serious and unexpected.
- Any finding from tests in laboratory animals that suggests a significant risk for human subjects including reports of mutagenicity, teratogenicity, or carcinogenicity.

The Investigator shall notify his/her IRB/EC promptly of these new serious and unexpected AE(s) or significant risks to subjects.

The Investigator must keep copies of all AE information, including correspondence with Celgene and the IRB/EC, on file.

7. Response Criteria

Baseline lesion assessments will be measured. At least 1 lesion greater than 1.5 cm must be documented during screening as per Section 2, Schedule of Study Assessments.

Efficacy assessments are scheduled to occur per the Schedule of Study Assessments, Section 2. Assessments for response will be done at approximately day 1 of every cycle. Response will also be done using CT scans, PET-CT and bone marrow biopsy after 3, 6, 9 and cycle 12.

Response and progression will be evaluated in this study using the International workshop standardized response criteria for non-Hodgkin's lymphomas (IWG) (23).

-and-

Instructions for interpreting response criteria for lesion evaluation and best overall response may be found in Appendix D, International workshop standardized response criteria for non-Hodgkin's lymphomas (IWG).

8. Protocol Amendments/Deviations

Protocol amendments

Any amendment to this protocol must be agreed to by the Principal Investigator and reviewed by Celgene. Amendments should only be submitted to IRB/EC after consideration of Celgene review. Written verification of IRB/EC approval will be obtained before any amendment is implemented.

Protocol deviations

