When an emergency occurs that requires a deviation from the protocol for a subject, a deviation will be made only for that subject. A decision will be made as soon as possible to determine whether or not the subject (for whom the deviation from protocol was effected) is to continue in the study. The subject's medical records will completely describe the deviation from the protocol and state the reasons for such deviation. In addition, the Investigator will notify the IRB/EC in writing of such deviation from protocol.

9. Data Management

Analyses and Reporting

Data will be analyzed and reported after all subjects have been assessed for overall response after 3 cycles. All subsequent data collected will be analyzed and reported in a follow-up clinical report.

Study monitoring and auditing

Investigator responsibilities

Investigator responsibilities are set out in the ICH guideline for Good Clinical Practice (GCP) and in the US Code of Federal Regulations.

Investigators must enter study data into MDACC's PDMS. The Investigator will permit study-related monitoring visits and audits by MDACC's ORERM, Celgene or its representatives, IRB/EC review, and regulatory inspection(s) (e.g., FDA, EMEA, TPP), providing direct access to the facilities where the study took place, to source documents, to CRFs, and to all other study documents.

The Investigator, or a designated member of the Investigator's staff, must be available at some time during monitoring visits to review data and resolve any queries and to allow direct access to the subject's records (e.g., medical records, office charts, hospital charts, and study related charts) for source data verification. The data collection must be

completed prior to each visit and be made available to MDACC ORERM and the Celgene representative so that the accuracy and completeness may be checked.

The Investigator will be responsible for reviewing the data and determining the stopping rule.

10. Biostatistical Analysis

Overview

This is an open label, phase II clinical trial to evaluate the efficacy and safety of Lenalidomide given in combination with Ritximab to patients with indolent non-Hodgkin's lymphoma.

Datasets to be analyzed

Statistical Methodology

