The trial consists of 4 parallel patient cohorts. Using dose schedule A we will enroll 50 patients with follicular lymphoma (cohort 1) and 30 patients with marginal zone lymphoma (cohort 2). We will enroll 45 patients with small lymphocytic lymphoma (cohort 3). We will also enroll 30 patients with follicular lymphoma patients and treat them with dosing schedule B (cohort 4). This will allow the investigators to better characterize and define possible differences in the response rate and toxicity profiles for each of the study subgroups.

The overall response, denoted as OR (to be assessed at the end of 3 cycles), and toxicity (to be assessed at the end of the first cycle) will be monitored simultaneously for each of the subgroups separately using the Bayesian approach of Thall, Simon, Estey (1995, 1996) as extended by Thall and Sung (1998). Toxicity is defined as any grade 3 or 4 nonhematologic toxicity.

Cohort 1: For the subgroup of patients with follicular lymphoma and treated with dosing schedule A, historical data on similar patients show an overall response rate of 70% and toxicity rate of 20%. However, the information was down-weighted to reflect the same marginal OR and toxicity rates in 10 patients. Independence was assumed between OR and toxicity. It is expected for the current trial that the two-drug combination will improve the OR rate to 80% while the toxicity rate is maintained at 30%. A sample size of 50 patients ensures that, if the trial is not terminated early, a posterior 90% credibility interval for overall response rate will have width of 0.19 at most, under the assumption of an 80% of overall response rate. The probabilities of OR and toxicity for the historical data are modeled by beta distributions (Beta(7, 3) and Beta(2, 8), respectively). The prior probabilities of OR and toxicity for the experimental regimen are also modeled by beta distributions

(Beta(1.4, 0.6)) and Beta(0.4, 1.6), respectively), which have the same *means* as the corresponding beta distributions for the historical data. Denoting the historical probabilities of overall response rate and toxicity rate by {p(OR,H), p(TOX,H)}, the following decision criteria will be applied:

- 1) Let E correspond to the experimental treatment, stop if $Prob\{p(OR,H) + \delta_{OR} > p(OR,E) \mid data\} > 0.90$, where $\delta_{OR} = 0.1$
- 2) Stop if Prob{p(TOX,H) + δ_{TOX} < p(TOX,E)| data}>0.90, where δ_{TOX} =0.1

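### Does the missing time point for the primary response endpoint leave the primary result open to choice?

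*Combined protocol and SAP*

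**What the plan says.** The synopsis of the combined protocol and SAP gives the endpoint as "Primary: To determine the number of CR, PR, and progression-free survival". Section 4 gives it as "To determine the number of CR, and PR". Neither carries a time point, a window or a best-response rule. The primary objective is the overall response rate, also untimed, and the Analysis Plan (numbered 11.3) speaks only of the response rate.

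Two places attach a time to the term overall response, and they agree. Section 10, Statistical Methodology, has "The overall response, denoted as OR (to be assessed at the end of 3 cycles". Section 9, Analyses and Reporting, ties the first analysis to the same assessment ("Data will be analyzed and reported after all subjects have been assessed for overall response after 3 cycles") and adds "All subsequent data collected will be analyzed and reported in a follow-up clinical report".

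Response is also measured later. Section 7 states "Response will also be done using CT scans, PET-CT and bone marrow biopsy after 3, 6, 9 and cycle 12", and section 5 schedules assessments after cycles 3 and 6, with cycles 9 and 12 for patients on extended dosing. Best overall response is named once, in a pointer: "Instructions for interpreting response criteria for lesion evaluation and best overall response may be found in Appendix D". That appendix is not in the text supplied, so nothing is inferred from it.

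**The concern.** Cycle 3 is half of the 6 cycles planned in Schedule A and a quarter of the 12 in Schedule B. Patients with stable disease at cycle 3 continue treatment, so some may respond later. They would be non-responders at cycle 3 and responders on a best-response count. The documents give some reason to expect this. Section 5 cites a response-rate benefit from extended dosing, and section 3 describes two responses at four months on monotherapy in relapsed or refractory indolent disease.

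The trial is open label, and section 9 says "The Investigator will be responsible for reviewing the data and determining the stopping rule". Section 3 also gives a preliminary response rate, apparently from this trial, of 85% in 13 evaluable patients with no time attached. If the label primary were free, it could be attached to the more favourable rate once cycle-3 data were known. The gap between historical and target response is only 10 points (70% to 80%, or 50% to 60% in small lymphocytic lymphoma), so the choice of window might decide whether a cohort appears to reach its target.

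**Working it through.** **1. Do the design figures hold together?**

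Inputs from section 10: prior Beta(1.4, 0.6) for response in cohorts 1, 2 and 4 and Beta(1, 1) in cohort 3; sample sizes 50, 30, 30 and 45; assumed response 80%, or 60% in cohort 3. The posterior is Beta(a + responders, b + non-responders), and the interval runs from its 5th to its 95th percentile.

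| Cohort | Responders | Posterior | 90% interval | Width | Stated |
|---|---|---|---|---|---|
| 1 | 40/50 | Beta(41.4, 10.6) | 0.699 to 0.880 | 0.181 | at most 0.19 |
| 2 and 4 | 24/30 | Beta(25.4, 6.6) | 0.668 to 0.898 | 0.230 | 0.23 |
| 3 | 27/45 | Beta(28, 19) | 0.477 to 0.710 | 0.233 | 0.23 |

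All the printed response and toxicity boundaries are reproduced exactly with a margin of 0.1. All the printed early-stopping probabilities are reproduced within 0.7 percentage points when the look at the maximum sample size is not counted as early. The design is coherent for one binary response per patient, and the only time given for that response is the end of cycle 3.

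**2. What can be reported at the planned first analysis?**

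Section 9 starts that analysis once every patient has a cycle-3 assessment. The last patients enrolled then have no later assessment. Cycle-3 response is therefore the scheduled response measure that is complete for the whole trial at that moment. A cycle-6 rate would need a further 3 × 28 = 84 days, or 12 weeks.

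**3. How far apart could the two rates be?**

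Let p be the cycle-3 rate and g the share of cycle-3 non-responders who respond later. The documents give no value for g. Best response is p + (1 − p)g.

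| p | g = 0 | g = 10% | g = 25% | g = 50% |
|---|---|---|---|---|
| 0.70 | 0.70 | 0.73 | 0.775 | 0.85 |
| 0.50 | 0.50 | 0.55 | 0.625 | 0.75 |

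A 10-point gap needs g = 0.10/0.30 = 33% from p = 0.70, and g = 0.10/0.50 = 20% from p = 0.50. If a third of the non-responders had already progressed and stopped (an assumption), the remaining patients would have to convert at 10/20 = 50% and 10/33.3 = 30%.

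**4. Two contrasts that look telling but are not.**

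- At 35/50 the cohort 1 interval is 0.592 to 0.799, width 0.207. This does not breach the stated 0.19, which is given only for 80% response. An interval around 70% is wider for the same sample size.
- At toxicity 0.30, cohort 1 stops early with probability 0.13 if true response is 0.80 and 0.35 if it is 0.70. These are two printed rows of the section 10 table. They show the rule responding to a lower cycle-3 rate, and relabelling the primary endpoint would leave both unchanged.

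**The case for a change.** The best argument for amending is that no sentence equates the primary endpoint with cycle-3 response. The section 10 sentence introduces interim monitoring, and the section 9 sentence is a reporting trigger. A plan may monitor on an early response and take best response as its primary result, and such a plan could contain the same two sentences. In an open-label trial with some response data apparently known, a fixed label is worth having, and it would cost one line. The historical rates of 70% and 50% have no stated time either. If they are best-response rates, a cycle-3 rate is being compared with a more generous measure.

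The missing line is real, and so is the silence on the historical rates. Both are gaps in detail. They do not show that the plan is open in practice, because no passage ties the primary endpoint to a later response. The line about the investigator concerns the stopping rule, not the choice of endpoint. Since the cycle-3 rate is reported first, a later substitution would be visible.

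The stronger remedy, best response by cycle 6 as primary, has costs of its own. It would replace the only stated time after response data were apparently seen, which is the hazard complained of. It would count responses that follow the dose change section 5 prescribes for cycle-3 non-responders, and so would measure a different treatment effect. It would delay the primary report by about 12 weeks and separate the primary estimate from the cycle-3 boundaries. A statistician could reasonably refuse it.

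**Conclusion.** No change to the plan follows. The primary endpoint lacks a printed time point in the synopsis and section 4, but sections 9 and 10 together point to the end of cycle 3. An analyst would fill the gap that way, report later response in the follow-up report, and be sound on both. Adding the words would be a courtesy to the reader; it would alter no sample size, boundary or operating characteristic if cycle 3 is named.

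The possible difference between the two rates ranges from zero to about 10 points only under an assumed share of late responders, up to 33% of cycle-3 non-responders (20% in small lymphocytic lymphoma). The support for late response is thin: two responders on monotherapy in relapsed or refractory disease, and a rationale drawn from chronic lymphocytic leukaemia and myeloma. The conclusion rests on reading sections 9 and 10 together. It would weaken if the unseen response-criteria appendix tied the primary endpoint to best overall response. The listing of progression-free survival as primary in the synopsis but not in section 4 is a separate matter and does not affect this one.

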11.3 Analysis Plan

Data from each of the patient subgroups will be analyzed separately. Summary statistics will be provided for continuous variables. Frequency tables will be used to summarize categorical variables. Logistic regression will be utilized to assess the effect of patient prognostic factors on the response rate and the toxicity rate. The distribution of time-to-event endpoints will be estimated using the method of Kaplan and Meier. Comparison of time-to-event endpoints by important subgroups will be made using the log-rank test. Cox proportional hazard regression will be employed for multivariate analysis on time-to-event outcomes.

11. Regulatory Considerations

Institutional Review Board/Ethics Committee approval

The protocol for this study has been designed in accordance with the general ethical principles outlined in the Declaration of Helsinki. The review of this protocol by the IRB/EC and the performance of all aspects of the study, including the methods used for obtaining informed consent, must also be in accordance with principles enunciated in the declaration, as well as ICH Guidelines, Title 21 of the Code of Federal Regulations (CFR), Part 50 Protection of Human Subjects and Part 56 Institutional Review Boards.

The Investigator will be responsible for preparing documents for submission to the relevant IRB/EC and obtaining written approval for this study. The approval will be obtained prior to the initiation of the study.

The approval for both the protocol and informed consent must specify the date of approval, protocol number and version, or amendment number.

Any amendments to the protocol after receipt of IRB/EC approval must be submitted by the Investigator to the IRB/EC for approval. The Investigator is also responsible for notifying the IRB/EC of any serious deviations from the protocol, or anything else that may involve added risk to subjects.

Any advertisements used to recruit subjects for the study must be reviewed and approved by the IRB/EC prior to use.

Informed consent

The Investigator must obtain informed consent of a subject or his/her designee prior to any study related procedures as per GCPs as set forth in the CFR and ICH guidelines.

Documentation that informed consent occurred prior to the subject's entry into the study and the informed consent process should be recorded in the subject's source documents. The original consent form, signed and dated by the subject and by the person consenting the subject prior to the subject's entry into the study, must be maintained in the Investigator's study files.

Subject confidentiality

Affirmed in MDACC informed consent document.

Study records requirements

The Investigator must ensure that the records and documents pertaining to the conduct of the study and the distribution of the study drug, that is copies of CRFs and source documents (original documents, data, and records [e.g., hospital records; SAE reports, clinical and office charts; laboratory notes; memoranda; subject's diaries or evaluation checklists; pharmacy dispensing records; recorded data from automated instruments; copies or transcriptions certified after verification as being accurate copies; microfiches; photographic negatives, microfilm, or magnetic media; x-rays; subject files; and records kept at the pharmacy, at the laboratories, and at medico-technical departments involved in the clinical study; documents regarding subject treatment and study drug accountability; original signed informed consents, etc.]) be retained by the Investigator for as long as needed to comply with national and international regulations (generally 2 years after discontinuing clinical development or after the last marketing approval). The

Investigator agrees to adhere to the document/records retention procedures by signing the protocol.

Premature discontinuation of study

Single center

The responsible local clinical Investigator as well as Celgene have the right to discontinue this study at any time for reasonable medical or administrative reasons in any single center. Possible reasons for termination of the study could be but are not limited to:

- Unsatisfactory enrollment with respect to quantity or quality.
- Inaccurate or incomplete data collection.
- Falsification of records.
- Failure to adhere to the study protocol.

Study as a whole

Celgene reserves the right to terminate this clinical study at any time for reasonable medical or administrative reasons.

Any possible premature discontinuation would be documented adequately with reasons being stated, and information would have to be issued according to local requirements (e.g., IRB/EC, regulatory authorities, etc.).

12. References

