Several phase II studies have shown activity with lenalidomide in CLL. Higher doses (25mg) have been associated with increased toxicity in the form of an increased incidence of tumor flare and tumor lysis syndrome (TLS).27,28 Tumor flare has also been correlated with response and may be associated with lenalidomide efficacy. 29 However, lower doses (10mg) appear to be better tolerated and have been associated with fewer cases of tumor flare. Ferrajoli et al treated 35 patients with CLL with a starting dose of 10mg daily for 28 days with a dose escalation to 25mg as tolerated. There were no cases of tumor lysis reported, and only 12% of patients developed tumor flare. The median dose level was 10mg. 30 In another phase II trial with lenalidomide in CLL, 2 out of the first 25 patients experienced TLS at the initial starting dose level (25mg). The study was modified to begin at a lower starting dose and none of the 16 patients who started on the 10mg dose level experienced tumor lysis. The incidence of tumor flare was unchanged, but the severity of reactions decreased significantly.31

Response to therapy will be assessed after 3 cycles and after 6 cycles of chemotherapy. In patients that continue on with extended dosing beyond cycle 6, response will also be evaluated after 9 and 12 cycles of chemotherapy. If after 3 cycles of therapy, there is stable disease without progression, as defined by IWG criteria, the lenalidomide dose will be increased for a total daily dose of 25mg, or 5 mg above the current dose in patients with SLL. If there is evidence of progression of disease, the patient will discontinue study medication.

The rationale for schedule B is derived from studies in both CLL and multiple myeloma suggest a clinical benefit (response rate and PFS) with extended dosing of lenalidomide. In schedule B, the dose of lenalidomide will be reduced in responding patients on cycles 7-12 to minimize potential myelosupression with increased exposure. In addition, significant infusion reactions to rituximab have been noted to occur beyond cycle 2. Although etiology of the infusion reactions is unknown, the severity of the reaction may be potentiated by concurrent dosing of lenalidomide. Ancedotal experience suggests that starting lenalidomide on day 2 of treatment (rituximab on day 1) may lessen the observed toxicity. Dose intensification of rituximab (weekly dosing) will occur in cycle 1 to increase mean serum concentration early in treatment.

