In Schedule A, treatment will continue until six cycles or the occurrence, if it is determined by the treating physician that the patient will derive clinical benefit from

extended dosing. **In schedule B**, all patients will continue until 12 cycles or the occurrence of any of the following events.

Treatment with study drug is to be discontinued when any of the following occurs:

- Lack of therapeutic effect
- Adverse event(s) that, in the judgment of the Investigator, may cause severe or permanent harm or which rule out continuation of study drug.
- Major violation of the study protocol.
- Withdrawal of consent
- Lost to follow up
- Death
- Suspected pregnancy

Follow-Up

Subjects who discontinue treatment for any reason, will be followed for 6 months. Subjects will undergo a safety assessment approximately 28 days post the last dose of study drug. In addition, off study evaluations, such as recording subsequent therapy, per the Schedule of Assessments will be done. Following completion of chemotherapy, patients will be evaluated every 3 months for one year, every 6 months for 1 year and then yearly with CT of neck, thorax, abdomen and pelvis and other studies as recommend by the treating physician.

Correlative Studies:

The mechanism of action, as well as the effect on the target microenvironment of the combination of lenalidomide and rituximab is poorly understood. In vitro, lenalidomide has been shown to increase recruitment and activation of immune effector cells and potentially repair T cell recognition and killing of malignant cells. By measuring levels of immune effector cells in accessible lesions, and comparing these with pre-treatment biopsies, we will learn about potential mechanisms of action of lenalidomide in untreated NHL.

Using peripheral blood samples, we will measure the number and function of immune effector cell subsets on day 1 of cycle 1 (allowed up to 48 hours prior to treatment), day 1 prior to treatment on cycle 2, day 15 of cycle 2, and on day 28 (+/- 3 days) of cycle 6. We will also measure gene expression on PBMCs prior to treatment on day 1 (allowed up to 48 hours prior to treatment) and on day #15 of cycle 2.

An elective core needle biopsy of an accessible tumor will be obtained with the patient's consent on day 18 of cycle 1. The tumor composition will be examined for infiltration and levels of non-malignant B-cells, activated NK cells, and T-cell subsets.

6. Adverse events

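### Crude whole-treatment adverse event tables would set Schedule B (12 cycles planned for all) against Schedule A (6 cycles, 12 only on response or benefit) with no common window or exposure term

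*Combined protocol and SAP*

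**What the plan says.** **Aim.** Section 10, Statistical Methodology, says the cohorts will let the investigators "better characterize and define possible differences in the response rate and toxicity profiles for each of the study subgroups". The secondary endpoint in section 4 is: "Determine the type, frequency, severity, and relationship of adverse events to lenalidomide and rituximab". It has no time window.

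**Analysis.** Section 11.3 states "Data from each of the patient subgroups will be analyzed separately" and "Frequency tables will be used to summarize categorical variables". For modelling it adds: "Logistic regression will be utilized to assess the effect of patient prognostic factors on the response rate and the toxicity rate". It gives no exposure term, rate per cycle or common window.

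**Planned exposure.** Under Discontinuation of Study Treatment in section 5, for Schedule B, "all patients will continue until 12 cycles or the occurrence of any of the following events". Rituximab is given four times in cycle 1 and once in each later cycle. For Schedule A the same paragraph begins "In Schedule A, treatment will continue until six cycles or the occurrence" and goes on to allow extended dosing if the treating physician expects benefit. The synopsis ties extension to tumor response; section 5, Overall design, ties it to documented clinical benefit without progression. Drug Administration lists Schedule A rituximab on day 1 of cycles 1-12.

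**Why the schedules differ.** The rationale for Schedule B in section 5 notes that "significant infusion reactions to rituximab have been noted to occur beyond cycle 2" and reports, as anecdote, that starting lenalidomide on day 2 may lessen this. It also gives possible myelosuppression from longer exposure as the reason for lowering the lenalidomide dose in responding patients in cycles 7-12.

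**The concern.** A frequency table over the whole treatment period counts more events where patients are treated, and therefore observed, for longer. The Schedule of Study Assessments records adverse events at treatment visits and at discontinuation, and section 5 adds a safety assessment about 28 days after the last dose, so observation follows treatment. Every Schedule B patient is planned for 12 cycles. A Schedule A patient reaches 12 only by responding or benefiting, so exposure in A is both shorter on average and dependent on outcome.

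Cohorts 1 and 4 are both follicular lymphoma and differ by schedule, so their tables will be read side by side for the stated aim. Cohort 3 has the opposite problem: section 5 splits its 45 patients into 30 on A and 15 on B, while section 10 treats them as one group. At stake is whether a difference in the tables reflects the schedule or the length of treatment, especially for infusion reactions beyond cycle 2 and later myelosuppression.

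**Working it through.** **The plan's own figures.** The section 10 toxicity rule uses Beta(2, 8) for the historical rate, Beta(0.4, 1.6) for the prior on the experimental rate, a margin of 0.1 and a cut-off of 0.90. Recomputing it for cohort 4 gives boundaries of 4, 7, 9, 11, 14 and 16 at 5 to 30 patients, exactly as printed. At true toxicity 0.30 and response 0.80, early stopping is 0.129 (50,000 simulated trials) against the printed 0.13. This outcome is grade 3 or 4 nonhematologic toxicity assessed at the end of cycle 1 in every cohort, so later cycles cannot enter it.

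**Exposure from the documents**
- Schedule B: 12 cycles; infusions 4 + 11 = 15.
- Schedule A: 6 cycles and 6 infusions as the base; 12 and 12 if extended.
- Cycles 1-6 only: B has 4 + 5 = 9 infusions, A has 6.

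**Assumptions (not in the documents).** Constant, equal risk *q* per cycle or per infusion; planned treatment completed; share *c* of A patients extending to 12 cycles.

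**Formulas.** The chance of at least one event over *k* units is P(k) = 1 − (1 − q)^k. Schedule A gives (1 − c)·P(6) + c·P(12). Schedule B gives P(12) for cycles and P(15) for infusions.

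*Per cycle, q = 5%.* P(6) = 1 − 0.95^6 = 26.49%; P(12) = 1 − 0.95^12 = 45.96%.

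*Per infusion, q = 3%.* P(6) = 16.70%; P(12) = 30.62%; P(15) = 36.67%.

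| Share of A extending | A, per cycle | B, per cycle | Gap (points) | A, per infusion | B, per infusion | Gap (points) |
|---|---|---|---|---|---|---|
| 0% | 26.5% | 46.0% | 19.5 | 16.7% | 36.7% | 20.0 |
| 50% | 36.2% | 46.0% | 9.7 | 23.7% | 36.7% | 13.0 |
| 80% | 42.1% | 46.0% | 3.9 | 27.8% | 36.7% | 8.8 |
| 100% | 46.0% | 46.0% | 0 | 30.6% | 36.7% | 6.1 |

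Gaps are taken before rounding; for example, 36.67 − (0.2 × 16.70 + 0.8 × 30.62) = 36.67 − 27.83 = 8.84. The 80% row borrows the expected response rate in cohort 1 as an illustration only.

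**Range over the per-cycle risk.** At 1% per cycle the gap is 5.5 points with none extending and 1.1 with 80%. At 10% it is 24.9 and 5.0.

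**If reactions cluster at the first infusion.** Assume 55% at infusion 1 and 3% at each later one. Then 6 infusions give 1 − 0.45 × 0.97^5 = 61.4%, 12 give 1 − 0.45 × 0.97^11 = 67.8%, and 15 give 1 − 0.45 × 0.97^14 = 70.6%. The gap is 9.3 points with none extending, 4.1 with 80% (A = 0.2 × 61.36 + 0.8 × 67.81 = 66.52%) and 2.8 with all.

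**After the change.** In cycles 1-6, equal risk per cycle gives equal incidence (26.5% in both at 5%). For infusions the window alone is not enough: at 3%, 9 infusions give 1 − 0.97^9 = 24.0% against 16.7% for 6. A rate per infusion is 3% in both.

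**The case against.** The strongest reply has four parts.

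**Schedule A is not fixed at 6 cycles and 6 infusions.** A reader might set B's 12 and 15 against A's 6 and 6 and take the full 20-point gap as the expected error. The documents do not support that, because A can run to 12 and 12. If most A patients extend, the per-cycle gap is small. This stands, and the result has to be shown over the share extending.

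**The defined toxicity outcome is safe.** A reader might infer that the toxicity monitoring is biased. It is not, since the outcome closes at the end of cycle 1. B's four infusions in that cycle against one in A are part of the regimen, not a follow-up artefact. But this outcome cannot address infusion reactions beyond cycle 2, hematologic toxicity or anything later. Only the adverse event tables can.

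**Constant risk is doubtful.** Section 3, Adverse Events, says most subjects had infusion reactions at the first infusion. Lenalidomide is reduced in cycles 7-12 for some B patients, while Overall design keeps extended patients at the cycle 6 dose. Both could shrink the gap. This stands for its size. It is also a reason to show late cycles separately, because a cumulative table would hide a lower late risk.

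**No A versus B test is planned, and total burden is a legitimate summary.** Both are true: subgroups are analysed separately, the comparison is descriptive, and the documents describe no randomisation between schedules. Section 11.3 also does not say how adverse events are to be counted; patients with at least one event is the usual reading of a frequency table. Separate tables still serve the stated aim of defining differences, and nothing in section 11.3 guards that reading.

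**Conclusion.** The point holds as a gap in the analysis of the all-adverse-event secondary endpoint. Following section 11.3 as written leaves length of exposure mixed with schedule, and exposure in A depends on outcome. The direction is towards B looking more toxic at equal risk. The size depends on two quantities the documents do not give. At 5% per cycle it runs from 19.5 points to zero as the share of A extending goes from none to all. At 3% per infusion it runs from 20.0 to 6.1 points, and it is smaller if reactions are concentrated at the first infusion. The last 6.1 points come from B's extra cycle 1 infusions: they are real burden, but say nothing about risk per infusion.

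A reader might go further and infer that the tables would reverse the trial's conclusion about Schedule B. The documents do not support this. The infusion-reaction rationale is anecdotal, no hypothesis is attached to it, and whether a lower risk per infusion would be masked depends on unknown rates. This is a worthwhile, inexpensive improvement to a descriptive endpoint; it does not affect the response analysis or the stopping rules.

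**What to change.** In section 11.3, for any descriptive A versus B statement on toxicity:

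1. Tabulate adverse events by schedule, splitting cohort 3 into its 30 Schedule A and 15 Schedule B patients.
2. Use cycles 1-6 as the common window. Show cycles 7-12 separately, with the number of patients at risk.
3. Give infusion reactions per rituximab infusion, with cycle 1 separate from later cycles.
4. Give events per patient-cycle as a supplement.
5. Keep the whole-treatment table, labelled as total burden.

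The statements on Schedule A duration and extension (synopsis; section 5, Overall design, Drug Administration and Discontinuation of Study Treatment) must also be reconciled, because they define who is at risk in cycles 7-12.

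**Cost.** Analysis-plan wording and a few tables. Section 6 already asks for the duration of each adverse event episode and for dates and times of drug administration in adverse event reports, so no new patient assessments should be needed. The limitation is that rates per patient-cycle average over changing risk and over the selected patients who reach late cycles. They should therefore supplement the cycles 1-6 table, not replace it.
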